7.5.3. Expedited Reporting of Adverse Events

Sponsor Drug Safety, in compliance with 21 CFR 312.32, will be responsible for determining the expectedness of events suspected of being related to study treatments based on the Investigators Brochure, and will notify the SAHPRA and Investigators of any AEs that are suspected, unexpected, and serious as soon as possible but no later than the required 7 or 15 calendar days after Sponsor Drug Safety initial receipt of the information. As per SAHPRA guidance, Sponsor Drug Safety will notify SAHPRA and any other applicable party of any new information impacting the risk-benefit profile of the study treatment or conduct of the trial within 3 calendar days.

The Sponsor or its authorized representative shall notify the regulatory authorities and Investigators of the following information:

- Any serious and unexpected AE suspected of being related to the use of study treatment in this study or in other studies.
- Any finding from tests in laboratory animals that suggests a significant risk for human participants, including reports of mutagenicity, teratogenicity, or carcinogenicity.

Where required by local legislation, the Investigator is responsible for informing the IRB/IEC of the SAE and providing them with all relevant initial and follow-up information about the event. The Investigator must keep copies of all SAE information on file including correspondence with the Sponsor and the IRB/IEC.

7.6. Reporting of Pregnancy

7.6.1. Females of Childbearing Potential

Pregnancies and suspected pregnancies (including a positive pregnancy test regardless of age or disease state) of a female participant occurring during study participation are considered immediately reportable events. The study regimen is to be discontinued immediately. The pregnancy, suspected pregnancy, or positive pregnancy test must be reported to Sponsor Drug Safety immediately by facsimile, or other appropriate method, using the Initial Pregnancy Questionnaire Report Form. The female participant may be referred to an obstetrician-

gynecologist (not necessarily one with reproductive toxicity experience) or another appropriate healthcare professional for further evaluation.

Safety assessments including collection of AEs and concomitant medications should continue as scheduled in [Table 9](#) until completion of the study.

The Investigator will follow the female participant until completion of the pregnancy and must notify Sponsor Drug Safety immediately about the outcome of the pregnancy (either normal or abnormal outcome) using the Follow-up Pregnancy Report Form. The participant will be contacted up to six months following a live birth for information on the health of the child.

If the outcome of the pregnancy was abnormal (eg, spontaneous or therapeutic abortion), the Investigator should report the abnormal outcome as an AE. If the abnormal outcome meets any of the serious criteria, it must be reported as an SAE to Sponsor Drug Safety immediately by facsimile, email, or other appropriate method within 24 hours of the Investigator's knowledge of the event using the SAE Report Form.

All neonatal deaths that occur within 28 days of birth should be reported as SAEs, without regard to causality. In addition, any infant death after 28 days that the Investigator suspects is related to the in utero exposure to study drug should also be reported to Sponsor Drug Safety immediately by facsimile, email, or other appropriate method within 24 hours of the Investigator's knowledge of the event using the SAE Report Form.

7.6.2. Male Participants

If a female partner of a male participant receiving study treatment becomes pregnant within 1 month after the last dose of vaccine, the male participant receiving study treatment should notify the Investigator as soon as possible. The Investigator will provide a copy of the Pregnant Partner Informed consent form and a copy of the pregnancy questionnaire to the male study patient for delivery to the pregnant partner.

If the pregnant partner agrees, she will need to meet with study staff to further discuss the study and ask any questions she may have on the consent form or questionnaire, and sign the Pregnant Partner Informed Consent form in the presence of study staff. The pregnant partner will be contacted for information regarding the outcome of the pregnancy (eg, live birth, etc.) and will be contacted up to 6 months following a live birth for information on the health of the child.

If the pregnant partner refuses to consent, the Investigator will record that a pregnancy occurred and that the pregnant partner refused consent.

7.7. Safety Queries

Queries pertaining to SAEs will be communicated from Sponsor Drug Safety to the site via email or fax. The response time is expected to be no more than 5 business days. Urgent queries (eg, missing causality assessment) may be handled by phone.

7.8. Safety Oversight

Sponsor Drug Safety reviews SAEs as they are reported, and routinely reviews safety data monthly, including AEs, medical history, and concomitant medications, for trends which might suggest a safety signal. Detection of possible safety signals results in a review by the SRC, a cross-functional team. The SRC is responsible for determining if new safety information should result in modification or termination of the study.

7.8.1. Safety Review Committee

7.8.1.1. Safety Review Committee Members

The SRC will include the medical monitor, the Principal Investigator (or designee), Investigators of active sites as deemed appropriate, Pharmacovigilance staff, and at least one qualified infectious disease physician independent of the Sponsor and trial, and representatives of any other function as deemed necessary. Sponsor clinical operations personnel are responsible for organizing and documenting the meetings.

7.8.2. Phase 1 Study Toxicity Study Stopping Rules

Safety will be monitored throughout the study.

In the phase 1 study, the first 7 days after vaccine administration are defined as the toxicity assessment period. The SRC will also review each treatment-related SAE and toxicity, during the toxicity assessment period and each treatment-related SAE and grade ≥ 3 AE after the toxicity assessment period, to determine if the event warrants stopping the trial, modifying the trial, or continuing without modification. In the event of a death that is suspected to be related to the treatment regimen, further enrollment will be delayed until the SRC approves continuation of enrollment in order to allow for proper review and notification to the IRB and the SAHPRA. In the event of a pause in clinical trial enrollment due to toxicity, both the SRC and the SAHPRA will be notified.

Stopping/pausing guidelines are predefined criteria that halt the conduct of a study. Toxicities that may warrant stopping of the trial, based on SAHPRA guidance and with grading scales from the Guidance for Industry: Toxicity Grading Scale for Healthy Adult and Adolescent Volunteers Enrolled in Preventive Vaccine Clinical Trials (2007) (see [Section 7.1](#)), include the following:

1. If 1 or more participants experience a Grade 4 AE ([Section 7.1](#)), vital sign or laboratory abnormality that is judged related to study vaccine, all vaccinations will be suspended until a full safety review is performed.
2. If 3 or more participants report the same or similar Grade 3 solicited AE, unsolicited AE, or clinically relevant laboratory abnormality judged related to the study vaccine, all vaccinations will be suspended until a full safety review is performed.
3. The study will be halted (no new enrollments and no further investigational product administered until a full safety review and consultation with the health authorities completed) if one of the following occurs:
 - a. One participant experiences an SAE judged related to the study vaccine, or
 - b. There is a participant death judged related to the study vaccine.

If any of the halting rules are met, vaccination of participants will be suspended until after full review of safety data by the SRC. The Investigator must inform the Sponsor and IRB if any of the halting rules are met. The Sponsor then must inform the SRC and SAHPRA.

7.8.2.1. Planned Safety Review Committee Meetings

For each cohort in phase 1, after all 10 participants have completed the toxicity assessment period, the SRC will review safety results to determine if the event warrants stopping the trial, modifying the trial, or continuing without modification.

Enrollment into subsequent cohorts will be suspended for safety review if:

- a. ≥ 3 participants report a Grade 3 or above AE, vital sign or laboratory abnormality judged related to study vaccine (see [Section 7.1](#) for toxicity grading), or
- b. ≥ 1 participant reports a Grade 4 AE that is judged related to study vaccine

If safety concerns are identified for any cohort in phase 1, the phase 1 study may be closed to further enrollment, and phase 2 study may enroll using a lower dose of an saRNA-based vaccine, provided the SRC recommends it is safe to proceed.

In addition to planned SRC meetings, ad hoc SRC meetings will be called at any time to evaluate safety concerns throughout the trial.

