3. INVESTIGATIONAL PLAN

3.1. Study Design

This is a phase 1/2 open-label study assessing the safety, reactogenicity, and immunogenicity of saRNA COVID-19 boost vaccines in participants that have been previously vaccinated against or previously infected with COVID-19. Participants enrolled will include individuals previously vaccinated against COVID-19 or previously infected with COVID-19 > 3 months prior to enrollment. Previously unvaccinated/vaccinated status and previously uninfected/infected status will be established by medical history and by SARS-CoV-2 serology assessed in the prescreening visit.

The phase 1 study is a single arm, open-label study. The phase 2 is a randomized open-label study. For the phase 2 study, laboratory analyses of immunogenicity assessments will be performed blind to participants' vaccine treatment on study. In all study phases, SARS-CoV-2 serological status will be assessed in a prescreening visit.

Participants will be ≥ 18 years of age who are healthy or have medically-stable chronic diseases. The treatment regime is described in the sections that follow. The study schema is shown in [Figure 1](#).

Phase 1

In the phase 1 study, up to 60 previously vaccinated/infected participants will be enrolled in 6 separate cohorts to receive a single vaccine boost consisting of either the AAHI-SC2 or AAHI-SC3 vaccine. Dosing schedule, mode of administration, and dosage for phase 1 are indicated in [Table 4](#).

Table 4: Phase 1 Previously Vaccinated/Infected Dosing Schedule

Phase	Cohort	Participants	Vaccine	Dosing Schedule	Dosage
PHASE 1	1A	10	AAHI-SC2	Day 1	25 μ g IM
	1B	10	AAHI-SC2	Day 1	50 μ g IM
	1C	10	AAHI-SC2	Day 1	70 μ g IM
	2A	10	AAHI-SC3	Day 1	25 μ g IM
	2B	10	AAHI-SC3	Day 1	50 μ g IM
	2C	10	AAHI-SC3	Day 1	85 μ g IM

Safety will be assessed for all participants and will include monitoring of vital signs, and incidence and severity of AEs. Blood samples will be collected for hematology and chemistry analyses and urine samples will be collected for urinalysis. Toxicities will be graded using the

Guidance for Industry: Toxicity Grading Scale for Healthy Adult and Adolescent Volunteers Enrolled in Preventive Vaccine Clinical Trials (2007).

For each cohort in phase 1, after all 10 participants have completed the toxicity assessment period, the SRC will review safety results to determine if the event warrants stopping the trial, modifying the trial, or continuing without modification.

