5.1.5. Dosing and Administration

Participants will be administered vaccine in each study phase as described in [Section 3.1](#). Participants will be monitored for 30 minutes after each administration for immediate adverse reactions (ARs), and appropriate personnel and therapies will be available to respond to any immediate AR.

Toxicity study stopping rules are detailed in [Section 7.8.2](#).

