6.3.1. Solicited Local and Systemic Adverse Events

Solicited AEs will be captured at study visits and by a diary distributed to participants. Thermometers and rulers will be provided to participants for evaluating AEs. Text and/or phone reminders to complete the solicited AE diary may be provided to participants.

Solicited local AEs to be assessed include redness, firmness, swelling, pain or itching at the injection site, medication taken for pain after IM administration, tingling/numbness, and bleeding or bruising at the injection site after IM administration. Solicited systemic AEs to be assessed include chills, nausea, vomiting, diarrhea, headache, fatigue, myalgia, abdominal discomfort/pain, joint pain, and fever. The solicited AE diary may be either electronic diary (eDiary) or a paper diary, as available. A sample diary for collecting solicited AEs is provided in [Appendix 1](#).

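### Phase 1 schedules a 7-day SRC review of every cohort but does not make the next higher dose of the same product wait for it

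*Combined protocol and SAP*

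**What the plan says.** Section 3.1 states that "up to 60 previously vaccinated/infected participants will be enrolled in 6 separate cohorts". Table 4 lists them as three dose levels of each product, 10 participants each, one dose on day 1. It gives no opening order and no condition for opening a cohort.

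Section 7.8.2 says that "the first 7 days after vaccine administration are defined as the toxicity assessment period". Sections 3.1 and 7.8.2.1 both say, for each cohort, that "after all 10 participants have completed the toxicity assessment period, the SRC will review safety results", with three possible outcomes: stop, modify or continue.

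The next statement in 7.8.2.1 is conditional: "Enrollment into subsequent cohorts will be suspended for safety review if" (a) three or more participants have a related event of Grade 3 or above, or (b) one or more has a related Grade 4 AE.

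Section 7.8.2 adds study-level rules for a related Grade 4 event, three or more participants with the same or similar related Grade 3 event, a related SAE, or a related death: "If any of the halting rules are met, vaccination of participants will be suspended until after full review of safety data by the SRC". It also provides that "The SRC will also review each treatment-related SAE and toxicity, during the toxicity assessment period", and 7.8.2.1 allows ad hoc SRC meetings at any time.

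On dosing, section 5.1.5 says "Participants will be administered vaccine in each study phase as described in" section 3.1, and it refers to 7.8.2 for stopping rules.

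**The concern.** A cohort review protects the next cohort only if the next cohort waits for it. Here the review is scheduled, but every stated restraint on later cohorts needs an event or a count to set it off. A site that moved from 25 to 50 µg the day after the tenth participant was dosed, with no trigger met, would comply with the text.

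Two situations matter. First, one or two participants with related, non-serious Grade 3 events meet no count, yet this is the kind of result a cohort review exists to weigh before the dose goes up. Second, the triggers see only what has been reported. Section 6.3.1 says "The solicited AE diary may be either electronic diary (eDiary) or a paper diary, as available", and Appendix 1 tells the participant to bring the completed diary to the next clinic visit. After day 1 that is visit 2, on day 8. Table 10 lists no phase 1 contact in between, and text or phone reminders are optional. With a paper diary, a Grade 3 solicited event may first reach the site on day 8, after someone else has received the higher dose. Section 7.1 itself asks for very low tolerance of risk in healthy volunteers.

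**Working it through.** The protocol has no figure to reproduce here. The check is a reading of the text, followed by illustrations under stated assumptions.

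**Reading.** These are the places that could hold the next dose:

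- 3.1 and 7.8.2.1, cohort review: scheduled after 7 days; no statement that the next cohort waits.
- 7.8.2.1 (a) and (b): suspension only if a count is met.
- 7.8.2 halting rules: suspension only if a listed event occurs.
- 7.8.2, death suspected to be related: enrollment waits for SRC approval. This is the only place where approval is required before enrollment goes on.
- 5.1.5, Table 4 and Table 10: no order, stagger or hold.

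**Dose steps affected.** From Table 4: 50/25 = 2.0 and 70/50 = 1.4 for AAHI-SC2; 50/25 = 2.0 and 85/50 = 1.7 for AAHI-SC3.

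**How often the count is not met.** The protocol gives no event rates, so these are assumed. I count trigger (a) within one cohort and assume no Grade 4 or serious events. With n = 10, P(X ≥ 3) is 0.070, 0.322 and 0.617 at related Grade 3 rates of 10%, 20% and 30%. At 20%:

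- trigger (a) is not met in 1 − 0.322 = 68% of cohorts;
- exactly one or two participants are affected in 10 × 0.2 × 0.8⁹ + 45 × 0.2² × 0.8⁸ = 0.268 + 0.302 = 57% of cohorts;
- if only 5 of the 10 had reported when the next cohort opened, the trigger would have fired with probability 0.058 instead of 0.322.

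**How many could be dosed early.** The protocol gives no accrual rate or cohort order. Assume ascending doses, evenly spaced dosing, cohorts back to back and no suspension, with time 0 at the first lower dose. At 1 per day, lower doses fall at times 0 to 9 and the first higher dose at 10. By then the participants dosed at times 0 to 3 (four people) have completed 7 days and six have not. The last lower-dose participant reaches day 8 at 9 + 7 = 16, and higher doses at times 10 to 15 make six. If that visit falls on day 11 (the ±3-day window in Table 10, read as covering day 8), the time is 9 + 10 = 19 and the count is nine. The other rates follow in the same way, with pairs dosed daily at 2 per day:

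| Assumed rate per day, per product | Time of first higher dose | Lower-dose participants short of 7 days then | Higher doses before last one reaches day 8 | Before day 11 |
|---|---|---|---|---|
| 0.25 | 40 | 1 of 10 | 1 | 2 |
| 0.5 | 20 | 3 of 10 | 3 | 4 |
| 1 | 10 | 6 of 10 | 6 | 9 |
| 2 | 5 | 10 of 10 | 12 | 18 |

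In the last row, 12 is 10 at the second dose and 2 at the third; 18 is 10 and 8. With a mandatory hold every count is 0 for that product.

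**The case against.** The strongest reply is that the gate is implied. Criteria (a) and (b) stand under the heading for planned SRC meetings, directly after the cohort review sentence. Criterion (b) would largely duplicate the Grade 4 halting rule unless it served as a decision criterion for that meeting, and a review that can end in continuing fits cohorts opened in sequence. This reading is plausible and may be what the sponsor intends. It is not stated, though, and suspending enrollment for safety review is an odd phrase if enrollment could not have begun before a review. Intent does not bind a site; the sentence does.

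Second, the text read here is incomplete: it starts at section 3, Figure 1 is not shown, and section 5 is partial. A hold could be stated in one of those places. That limits the claim to the sections read, but 3.1 and 7.8.2.1 are the operative ones, and 5.1.5 sends dosing to 3.1.

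Third, existing controls reach much of the scenario. The SRC reviews each related toxicity in the 7 days without a count threshold, can stop or modify the trial, and can meet ad hoc. An eDiary or a participant's call would shorten the delay. All of this stands and reduces the risk. What remains is events not yet reported.

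Fourth, the exposure counts rest on assumed schedules. That also stands: the largest need 2 participants per day per product and a third dose level opened without review of either earlier one.

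A reader might infer that phase 1 has no safety control over escalation, or that the sponsor plans to escalate without review. The documents support neither: the halting rules are explicit, and the review of every cohort is scheduled.

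**Conclusion.** The point holds as a gap in the written rule. Sections 3.1 and 7.8.2.1 schedule the cohort review, but they let the next higher dose go ahead without it unless an event trigger has been met. All four dose steps (1.4 to 2.0 times the preceding dose) are affected.

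The conclusion rests on the text alone, and no assumed rate is needed for it. The table shows only how the size would vary: from 1 early higher dose at slow accrual to 12 at fast accrual before day 8. It does not forecast this trial. Because the halting rules and individual toxicity review are real protections, this is a change that should be made rather than a failure of safety oversight. Confidence is medium because a hold may be stated in parts not seen.

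**What to change.** Add to 7.8.2.1, and repeat in 3.1:

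> No participant will be dosed in the next higher-dose cohort of a product until the SRC has reviewed the 7-day data, including the solicited AE diaries, of the preceding dose of that product and recorded its agreement to proceed. Criteria (a) and (b) and the halting rules in 7.8.2 apply in addition.

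If Figure 1 or another section already states this hold, repeat it in 7.8.2.1 so that the operative section agrees.

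Cost: 7 days from the last lower dose to day 8, or 10 if the visit falls on day 11, plus the time to hold an SRC review that is already planned. Over the two steps of one product that is 2 × 7 = 14 to 2 × 10 = 20 days plus the two reviews. The text does not say how dosing of the two products is ordered, so no phase 1 total is given. If sites already wait, the cost is only the wording. Sample size, endpoints and analyses do not change.

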7.8.3. Phase 2 Safety Review Committee Review

The SRC will provide ongoing safety review in the phase 2 study. If the SRC detects a possible safety signal, the statistical team will provide support to the SRC for a full review. The SRC will determine if the event warrants stopping the trial, modifying the trial, or continuing without modification.

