Solicited local and systemic reactogenicity AEs will be collected using diaries for 7 days following study intervention (ie, administration of vaccine). Unsolicited AEs will be recorded in a diary from time of vaccination until 30 days after study intervention. Medically attended adverse events (MAAEs) and SAEs will be recorded for 6 months after study intervention (related MAAEs and SAEs will be recorded at any time).

Immunogenicity analyses will be conducted by collecting serum and PBMC samples from individual participants before and after vaccinations to test for humoral- and cell-mediated immune responses. Neutralizing antibodies will be assessed.

Phase 2

In the phase 2 study, up to 120 previously vaccinated/infected additional participants will be enrolled. Participants in phase 2 will be randomized 1:1:1:1 to receive Janssen or Pfizer-BioNTech vaccine (control arm), the AAHI SC2 vaccine (experimental arm 1), or the AAHI-SC3 vaccine (experimental arms 2 and 3). Dose levels for the AAHI-SC2 and AAHI-SC3 vaccines will be as determined in the phase 1 study. Randomization will be stratified by age (18 to 55 years or > 55 years), by previous infection (previously infected or not), and by HIV status (positive or negative). Treatment arms are shown in Table 5.

Table 5: Phase 2 Previously Vaccinated/Infected Dosing Schedule

Treatment Arm	Participants	Vaccine	Dosing schedule	Dosage
Control arm	30	EUA or approved vaccine	Day 1	Per prescribing information
Experimental arm 1	30	AAHI-SC2	Day 1	TBD: As determined in phase 1 study
Experimental arm 2	30	AAHI-SC3	Day 1	TBD: As determined in phase 1 study
Experimental arm 3	30	AAHI-SC3	Day 1 and day 29	TBD: As determined in phase 1 study

In addition to dosing visits described above, all participants in all phases of the study will have follow up study visits for data collection.

The SRC will provide ongoing safety review in the phase 2 study. If a possible safety signal is detected, the SRC will determine if the event warrants stopping the trial, modifying the trial, or continuing without modification.

Solicited local and systemic reactogenicity AEs will be collected using diaries for 7 days following study intervention (ie, administration of vaccine). Unsolicited AEs will be recorded in

a diary from time of vaccination until 30 days after study intervention. MAAEs and SAEs will be recorded for 6 months after study intervention (related MAAEs and SAEs will be recorded at any time).

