4.7. Premature Termination or Suspension of Study

This study may be temporarily suspended or prematurely terminated if there is sufficient reasonable cause. Written notification, documenting the reason for study suspension or termination, will be provided by the suspending or terminating party to the Investigators and the regulatory authorities. If the study is prematurely terminated or suspended, the Principal Investigator will promptly inform the IRB and will provide the reason(s) for the termination or suspension.

Circumstances that may warrant termination or suspension include, but are not limited to:

- Death that is suspected to be related to the treatment regimen
- Determination of unexpected, significant, or unacceptable risk to participants
- Insufficient compliance to protocol requirements
- Data that are not sufficiently complete and/or evaluable

The study may resume once concerns about safety, protocol compliance, and data quality are addressed and satisfy the Sponsor, the IRB, and/or the South African Health Products Regulatory Authority (SAHPRA).

AAHI-SC2 and AAHI-SC3

Clinical Trial Protocol: COVID-4.015 Version 4

ImmunityBio, Inc.

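### It is ambiguous whether the one-event dosing holds apply in phase 2: they sit under a Phase 1 heading, yet phase 2 carries 120 of 180 planned experimental injections and every second dose

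*Combined protocol and SAP*

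**What the plan says.** The mandatory holds are in the section headed "7.8.2. Phase 1 Study Toxicity Study Stopping Rules". Rule 1 applies when one or more participants have a Grade 4 AE, "vital sign or laboratory abnormality that is judged related to study vaccine, all vaccinations will be suspended until a full safety review is performed". Rule 3 applies after one related SAE or one related death. It begins "The study will be halted" and adds that there are to be no new enrollments and "no further investigational product administered until a full safety review and consultation with the health authorities completed". Both rules stop dosing first and review second.

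Phase 2 has its own section, 7.8.3. It provides for continuing SRC review, with statistical support if a signal appears, and then: "The SRC will determine if the event warrants stopping the trial, modifying the trial, or continuing without modification". It sets no event count and no hold, and it does not refer back to 7.8.2. The phase 2 part of section 3.1 matches it: "If a possible safety signal is detected, the SRC will determine if the event warrants stopping the trial, modifying the trial", or continuing unchanged. Section 4.7 covers the whole study but is permissive: "This study may be temporarily suspended or prematurely terminated if there is sufficient reasonable cause".

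Other text points the other way. Section 5.1.5 governs dosing in both phases and sends the reader to 7.8.2 for the stopping rules. Section 5.1.7 also cites 7.8.2 without naming a phase.

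**The concern.** A halting rule works only if the site knows at once whether it is bound by it. Suppose a phase 2 participant has a Grade 4 event judged related. An investigator who reads the headings finds no duty to stop vaccinating others until the SRC decides. An investigator who starts from 5.1.5 finds a duty to stop immediately. The same event could be handled in two ways under one protocol.

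Phase 2 is where most experimental dosing takes place, and it is the only place where anyone receives a second dose. Phase 1 participants get a single boost, so arm 3's day 29 injection is the first repeat dose in this trial. Section 7.1 says that enrolling healthy volunteers calls for very little tolerance of risk. The plan gives no reason why a single related Grade 4 event, SAE or death should stop dosing in phase 1 but not in phase 2.

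**Working it through.** **1. Counts.** Inputs are from sections 3.1, 3.2, 3.3.1 and 8.4.

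- Participants: 6 cohorts × 10 = 60 in phase 1; 4 arms × 30 = 120 in phase 2; total 180. This reproduces the plan's figure in section 3.2.
- Experimental injections: phase 1 = 6 × 10 × 1 = 60; phase 2 = 30 (arm 1) + 30 (arm 2) + 30 × 2 (arm 3) = 120; total 180. The match with 180 participants is a coincidence: 30 controls receive no experimental injection and 30 arm 3 participants receive two.
- Phase 2 share of experimental injections: 120/180 = 67%.
- Second doses: 30, all in arm 3.
- Experimental recipients: 60 in phase 1 and 90 in phase 2, so 90/150 = 60% are in phase 2.

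Enrollment is stated as up to these numbers, so they are planned maxima.

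**2. Does the text bind phase 2?**

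| Points to phase 1 only | Points to the whole study |
|---|---|
| Heading of 7.8.2 | 5.1.5, the dosing section for both phases, cites 7.8.2 |
| Subsection 7.8.2.1 deals with phase 1 cohort reviews | 5.1.7 cites 7.8.2 with no phase limit |
| 7.8.3 and 3.1 treat phase 2 separately, with SRC judgment only | Rule 1 covers all vaccinations; rule 3 halts the study |

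Within 7.8.2, the words limiting scope to phase 1 are attached to the 7-day toxicity assessment period, not to the numbered rules. Neither column settles the matter.

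**3. Does another provision hold dosing for other participants?**

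- 4.5: mandatory discontinuation for unacceptable toxicity, but only for the affected participant.
- 5.1.5: 30-minute observation, which detects immediate reactions.
- 7.5.2: SAEs reported to the Sponsor within 24 hours.
- 7.8: SAEs reviewed as they are reported; possible signals go to the SRC; other safety data are reviewed monthly.
- 7.5.3: SAHPRA told within 3 calendar days of new information affecting risk-benefit.
- 7.8.2.1: "ad hoc SRC meetings will be called at any time to evaluate safety concerns throughout the trial".
- Table 10: a day 36 telephone call for arm 3.
- 4.7: suspension is possible but not required.

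These speed detection and decision. None clearly stops injections in other participants meanwhile.

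**4. Grade 4 events that are not SAEs.** In the section 7.1 tables, Grade 4 for most local and systemic reactions means an ER visit or hospitalization, and much of that would already meet the SAE criteria in 7.3. What remains is chiefly laboratory values (for example potassium above 5.6 mEq/L) and ER visits without admission. Section 7.2 makes a laboratory abnormality an SAE only if it meets a seriousness criterion. It also ties MAAEs to the criteria and collection guidelines in 7.3, but 7.3 sets no reporting deadline; the 24 hours are in 7.5.2, for SAEs.

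**5. How often would a phase 2 hold be triggered?** The documents give no event rate. With an assumed per-participant probability p of a related Grade 4 event or SAE, the chance of at least one among n recipients is 1 − (1 − p)^n.

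| Assumed p | Phase 2 (n = 90) | Phase 1 (n = 60) |
|---|---|---|
| 0.1% | 8.6% | 5.8% |
| 1% | 60% | 45% |
| 3% | 94% | 84% |

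This illustrates the cost of the fix. It is not evidence for the concern.

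**The case against.** The strongest reply is that the rules already reach phase 2. The dosing section for both phases names 7.8.2 as the place for stopping rules and names no other. The rule text is study-wide, and a heading should not override it. That reading is reasonable, and it is why the point is ambiguity and not a proven omission. It does not close the matter, because the plan also gives phase 2 its own section with a different, discretionary process and no link to 7.8.2.

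A second reply is that SRC discretion is a legitimate phase 2 choice: doses will have been chosen in phase 1, the SRC includes an independent infectious disease physician, and automatic holds could be frequent if related events are common. This stands as an argument about cost. The phase 1 column in step 5 shows, however, that at the same assumed rates the sponsor has already accepted pauses of similar likelihood.

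A third reply is that few Grade 4 events would escape the SAE process. That is correct, and the reporting gap should be described as narrow.

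A reader might infer that phase 2 has no stopping protection at all. The documents do not support that: 4.5, 4.7, 7.5.2, 7.5.3, 7.8 and the SRC all operate there, and 7.8.2 may apply too. A reader might also want the number of injections that would be given while the SRC deliberates. That needs an event rate, an enrollment pace, an onset time and a decision time, none of which is given. It would also have to be compared with a hold that itself takes time to trigger. No such figure should be quoted.

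**Conclusion.** The concern holds as an ambiguity of scope. Read by its headings, the plan lets experimental dosing continue in phase 2 while a related Grade 4 event, SAE or death is reviewed; read by its cross-references and rule wording, it does not. No other provision clearly supplies the hold. What is at stake is up to 120 of 180 experimental injections (67%) and all 30 second doses; these counts follow from the plan and need no assumption. The participants actually exposed by the ambiguity cannot be counted from the documents. This is a cheap improvement for the sponsor to consider, not a demonstrated failure of safety oversight.

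**What to change.** State in 7.8.3, or by changing the heading of 7.8.2, that rules 1 and 3 apply to phase 2 experimental arms 1 to 3:

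- A related Grade 4 event suspends AAHI-SC2 and AAHI-SC3 injections, including arm 3's day 29 dose, until full SRC review.
- A related SAE or death also requires consultation with the health authorities before restart.
- A day 29 dose delayed by a pause is either given late or omitted; say which.
- Related Grade 4 events that are not SAEs are reported to the Sponsor within 24 hours.

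Align 5.1.5 and 5.1.7 with this text. If the heading route is chosen, rule 2 (three same or similar related Grade 3 events) would come along with it, so say whether that is intended. Control injections need not be held, since the trial is open-label.

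The change is one amendment paragraph, with no new visits or assays. The real cost is pauses, whose likelihood depends on an event rate that the documents do not give. A pause during day 29 dosing could also push some second doses out of window. Table 10 shows ±3 days for the initial follow-up period, but its columns are broken in the text available, so whether that covers day 29 should be checked.
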